6.8. Infusion or Injection Site Reactions (ISR)

ISR is a type of hypersensitivity reaction that may be immediate, although it usually appears within 24-48 hrs after injection. ISR, by definition, includes the following: erythema, induration ecchymosis, pain and pruritus at the infusion or injection site.

Infusion or injection-related reactions will be assessed and managed based on the CTCAE severity scale for infusion reactions (see [Appendix 11](#)).

- Grade 1 reaction (Mild): Participant will be monitored closely at bedside while infusion or injection continues. For IV dosing, the PI may slow the infusion rate, based on medical judgement.
- Grade 2 (Moderate): Infusion may be paused, and symptomatic treatment (such as antihistamine, acetaminophen or nonsteroidal anti-inflammatory drugs (NSAIDs)) may be administered. For IV dosing, if the infusion is paused, once symptoms subside, infusion may be restarted at a 50% reduction in infusion rate. Infusion rate may be increased after 30 minutes if participant is stable.
- Grade 3 (Severe) or 4 (life-threatening): For IV dosing, the infusion will be stopped promptly. Participant will be followed until symptoms resolve, and no further follow-up regarding the AEs is needed in the opinion of the PI.
- For IV dosing, acute infusion reactions of mild-moderate severity (Grade 1 or Grade 2) which fully resolve following dose interruption and/or the administration of antihistamines/antipyretics with subsequent resumption and safe completion of dosing will not be considered dose limiting.

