Physical examination ^g	X	X																X	X	X	X	X	X	X	X			

Table 1. Schedule of Activities for IV cohorts

Protocol Activity	Screen		Clinical Confinement														Outpatient Follow-Up Visits										
	-56 to -2	-1 ^a	1														2	3	4	6	8	11 ±2	15 ±2	22 ±2	29 ±2	36 ^a ±3	50 ^a ±3
Hour(s) Post Dose			0 pre-dose	0.5	1 or EOI ^b	3 or EOI ^c	3.5	4	5	6	8	12	24	36	48	72	120	168	240	336	504	672	840	1176	1680		
Hematology & Coagulation (PT, INR, PTT, D-dimer & fibrinogen)	X	X			X ^{m,n}	X ⁿ			X ⁿ		X ⁿ	X ⁿ	X		X ⁿ	X	X	X	X	X	X	X	X	X	X		
Safety Labs					X ^{m,n}								X			X	X	X	X	X	X	X	X	X	X		
Chemistry/Urinalysis/Other Safety Labs	X	X			X ^{m,n}								X			X	X	X	X	X	X	X	X	X	X		
ECG ^h	X		X		X	X			X			X	X		X	X	X	X	X		X		X		X		
Telemetry		X ⁱ	X ⁱ	→	→	→	→	→	→	→	X																
Vital signs (BP, pulse rate, temperature) ^j	X		X	X	X	X	X ⁿ	X ⁿ	X	X ⁿ	X	X	X	X	X	X	X	X	X	X	X	X	X ⁿ	X	X ⁿ	X	
Pulse Oximetry	X		X	X	X	X	X ⁿ	X ⁿ	X	X ⁿ	X	X	X	X	X	X	X	X	X	X	X	X	X ⁿ	X	X ⁿ	X	
ADA blood sampling	X ^o	X																X		X			X		X		
CCI			█	█	█	█			█				█		█	█		█		█			█		█		
IV administration			X ^l	→	X	X																					
Infusion site assessment			X	X	X	X	X ⁿ	X ⁿ	X	X ⁿ	X	X	X					X ⁿ		X ⁿ			X ⁿ		X ⁿ		
PK blood sampling (IV Cohorts 1 and 2 only)			X		X	X			X		X	X	X	X	X	X	X	X									
PK blood sampling (IV Cohorts 3-5)			X		X	X			X		X	X	X		X	X	X	X		X	X	X	X	X	X		
PK blood sampling (IV Cohorts 5 exp. 6-9, and optional IV cohorts)			X		X ^{m,n}	X	X ⁿ	X ⁿ	X	X ⁿ	X	X	X		X	X	X	X		X	X	X	X	X	X		
Serious and non-serious Adverse Event monitoring	X	X	→	→	→	→	→	→	→	→	→	→	→	→	→	→	→	→	→	→	→	→	→	→	X		
Prior/Concomitant treatments	X	X	X										X	→	→	→	→	→	→	→	→	→	→	→	X		

Abbreviations: →= ongoing/continuous; ADA= anti-drug antibody; BP = blood pressure; ECG = electrocardiogram; EOI = end of infusion; HepBsAg = hepatitis B surface antigen; HepBcAb = hepatitis B core antibody; HCVAb = hepatitis C antibody; HIV = human immunodeficiency virus; IgA = immunoglobulin A; IgG = immunoglobulin G; INR = international normalized ratio; IV = intravenous; PK = pharmacokinetics; PT = prothrombin time; PTT = partial thromboplastin time; RNA = ribonucleic acid; TB = tuberculosis; T3 = triiodothyronine; T4 = thyroxine; TSH = thyroid stimulating hormone; TSAb = thyroid stimulating antibodies.

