Medication history	X	X ^c																										
Weight	X	X																							X		X	
Urine drug screening	X	X																										
FSH ^b	X																											
Serum Pregnancy ⁱ	X	X																										
Review contraception use	X	X																	X	X	X	X	X	X	X	X	X	
Physical examination ^d	X	X																	X	X	X	X	X	X	X	X	X	
Hematology & Coagulation (PT, INR, PTT, D-dimer & fibrinogen) Safety Labs	X	X										X	X		X	X		X	X	X	X	X	X	X	X	X	X	
Chemistry/Urinalysis/Other Safety Labs	X	X										X	X		X	X		X	X	X	X	X	X	X	X	X	X	

Table 3. Schedule of Activities for SC Cohorts of ITP Participants

Protocol Activity Abbreviations used in this table may be found in 10.14. Appendix 14: Abbreviations	Screen		Clinical Confinement																Outpatient Follow-Up Visits								
	-56 to -2	-1 ^a	1											2	3	4	5	6	8	11 ±2	15 ±2	22 ±2	29 ±2	36 ±3	50 ±3	71 ±3 or ET	
Hour(s) Post Dose			0 pre-dose	0.5	1	3	3.5	4	5	6	8	12	24	36	48	72	96	120	168	240	336	504	672	840	1176	1680	
ECG ^e	X		X						X		X	X		X	X		X	X	X		X		X		X		
Vital signs (BP, pulse rate, temperature) ^f	X		X						X		X	X	X	X	X		X	X	X	X	X	X	X	X	X	X	
Pulse Oximetry	X		X	X	X	X	X	X	X	X	X	X	X	X	X		X	X	X	X	X	X	X	X	X	X	
ADA blood sampling		X																	X		X			X		X	
CCI																											
SC Administration			X																								
SC Injection site assessment			X	X	X	X	X	X	X	X	X	X	X						X		X				X		X
PK blood sampling			X						X		X	X		X	X	X	X	X	X	X	X	X	X	X	X	X	
Urine pregnancy test ^g			X																					X		X	
Serious and non-serious Adverse Event monitoring	X	X	→	→	→	→	→	→	→	→	→	→	→	→	→	→	→	→	→	→	→	→	→	→	→	→	X
Prior/Concomitant treatments	X	X	X									X	→	→	→	→	→	→	→	→	→	→	→	→	→	→	X

Abbreviations: →= ongoing/continuous; ADA= anti-drug antibody; BP = blood pressure; ECG = electrocardiogram; HepBsAg = hepatitis B surface antigen; HepBcAb = hepatitis B core antibody; HCVA b = hepatitis C antibody; HIV = human immunodeficiency virus; IgA = immunoglobulin A; IgG = immunoglobulin G; INR = international normalized ratio; PK = pharmacokinetics; PT = prothrombin time; PTT = partial thromboplastin time; RNA = ribonucleic acid; SC = subcutaneous; TB = tuberculosis; T3 = triiodothyronine; T4 = thyroxine; TSH = thyroid stimulating hormone; TSAb = thyroid stimulating antibodies.

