6.6. Dose Progression

The participants within each cohort will be dosed using a sequential dosing scheme. For all cohorts, a single participant will be dosed at a given time, followed by a minimum of 72-hour (for IV) and 96-hours (for SC) safety monitoring period. In total there will be a minimum of 96 hours between each IV participant dosed and 120 hours for each SC participant dosed.

The following rules will be applied when considering dosing of the next participant in the cohort.

Sequential dosing may **proceed** only if no adverse events are reported OR all of the following criteria are met:

1. Any pro-inflammatory events are < Grade 2 Per CTCAE criteria in [Appendix 9](#).
2. All other adverse events are deemed mild or moderate in severity, regardless of relatedness.
3. Any laboratory, ECG or vital sign changes are considered not clinically significant.
4. No other pause or stop criteria are met.
5. For participants with ITP, in addition to the above criteria, no participant has greater than a 30% decrease in platelet count – defined from the immediate pre-dosing platelet count to the lowest postdosing platelet count. Dose progression will be independent of dose progression from HP cohorts at higher dose levels.

Sequential dosing should be **paused** if any criterion below is met in a participant receiving active drug:

1. Grade 2 (Objective) pro-inflammatory event (vomiting, diarrhea, hypotension or hypoxia) (see [Appendix 9](#)).
2. Adverse event which is considered to be severe (Grade 3 or higher) AND is deemed related to study intervention.
3. A moderate event (Grade 2) AND is deemed related to study intervention not otherwise identified as a proinflammatory event or AE of special interest, that in the opinion of the PI and Sponsor are of concern and warrant further investigation before additional dosing.
4. For participants with ITP, platelet count of <30 x 10⁹/L AND a decrease from baseline ≥30%, or a platelet count decrease from baseline of ≥50%, defined from the immediate pre-dosing platelet count to the lowest post-dosing platelet count, or a bleeding or bruising-related AE CTCAE 4.03 Grade 2 or higher (except metrorrhagia Grade 3 or higher).

Sequential dosing should be **stopped** at the current dose level if any criterion below is met in participant receiving active drug:

1. Grade 3 or greater pro-inflammatory event.
2. Serious adverse event that is deemed related to study intervention.

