8.3. Adverse Events and Serious Adverse Events

The definition of an AE and an SAE can be found in [Appendix 3](#).

AEs will be reported by the participant (or, when appropriate, by a caregiver, surrogate, or the participants legally authorized representative).

The investigator and any qualified designees are responsible for detecting, documenting, and recording events that meet the definition of an AE or SAE and remain responsible to pursue and obtain adequate information both to determine the outcome and to assess whether it meets the criteria for classification as an SAE or that caused the participant to discontinue the study (see [Section 7](#)).

Each participant will be questioned about the occurrence of AEs in a nonleading manner.

In addition, the investigator may be requested by Pfizer Safety to obtain specific follow-up information in an expedited fashion.

Assessment of adverse events will include the type, incidence, severity (CTCAE version 4.03, [Appendix 11](#)) timing, seriousness, and relatedness for injection site reactions. The severity of CRS will be assessed according to the grading described by the ASTCT and Lee et al. (2019, see [Appendix 10](#)).¹²

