10.11. Appendix 11: CTCAE (version 4.03) Grading System for Infusion-Related Reactions

Adverse Event	Grade 1	Grade 2	Grade 3	Grade 4	Grade 5
Infusion related reaction	Mild transient reaction; infusion interruption not indicated; intervention not indicated	Therapy or infusion interruption indicated but responds promptly to symptomatic treatment (eg, antihistamines, NSAIDS, narcotics, IV fluids); ^a prophylactic medications indicated for ≤24 hrs	Prolonged (eg, not rapidly responsive to symptomatic medication and/or brief interruption of infusion); recurrence of symptoms following initial improvement; hospitalization indicated for clinical sequelae	Life-threatening consequences; urgent intervention indicated	Death

a. Investigator may pause the infusion if needed in the case of an infusion related reaction, and apply prophylactic treatment after the event has resolved, order to mitigate against additional infusion related symptoms if/once the infusion was restarted.

Abbreviations: NSAID = non-steroidal anti-inflammatory drug; IV = intravenous.

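### No SC injection-site assessment is scheduled between 24 h and 168 h, although the protocol expects reactions at 24-48 h; the grade for local site signs also needs reconciling

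*Protocol*

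**What the plan says.** **Onset and definition.** Section 6.8 of the protocol says: "ISR is a type of hypersensitivity reaction that may be immediate, although it usually appears within 24-48 hrs after injection". It defines the event by local signs: "ISR, by definition, includes the following: erythema, induration ecchymosis, pain and pruritus at the infusion or injection site".

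**Schedule.** The row "SC Injection site assessment" appears in Table 2 (healthy participants), Table 3 (ITP) and Table 14 (ITP, Czech Republic). In all three it is marked at every time point from pre-dose to 24 h, is blank at 36, 48, 72, 96 and 120 h, and is marked again at 168 h (Day 8).

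**Review before the next participant.** Section 6.6 has each participant dosed singly, "followed by a minimum of 72-hour (for IV) and 96-hours (for SC) safety monitoring period". Section 4.1 attributes the longer SC period to preliminary data from Cohort 7.

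**Grading.** Section 6.8 says: "Infusion or injection-related reactions will be assessed and managed based on the CTCAE severity scale for infusion reactions". Section 8.3 lists type, incidence, severity (CTCAE 4.03, Appendix 11), "timing, seriousness, and relatedness for injection site reactions". Appendix 11 has one row, for infusion-related reactions, and its Grade 1 reads: "Mild transient reaction; infusion interruption not indicated; intervention not indicated". Appendix 3 separately requires a mild, moderate or severe intensity for each AE. Section 6.6 gives ITP participants a pause criterion for bleeding or bruising AEs graded by CTCAE 4.03.

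**The concern.** The protocol names the period in which it expects injection-site reactions, and the schedule stops looking as that period opens. Table 1 (IV) has the same pattern for "Infusion site assessment": last early mark at 24 h, next at 168 h. The SC safety review was extended to 96 h; the site-assessment row was not extended with it.

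Section 2.1 says no further IV dosing will occur, so SC local tolerability is part of the primary safety objective for every remaining cohort. Sections 2.1 and 2.3 name injection-site bleeding or bruising as a risk in ITP. The ITP cohorts are open-label without placebo, so there is no concurrent group in which under-recording would show. Section 8.3 asks for incidence and timing of these reactions, and both depend on when someone looks.

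The grading instructions raise a second question. The event is defined by local signs but referred to a table that describes none of them, while two other parts of the protocol also supply a severity scale that could apply.

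**Working it through.** There is no sample-size or error-rate figure to reproduce. The check matches each site-assessment row to its own hour header.

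| Schedule | Marks from 0 to 24 h | 36, 48, 72, 96, 120 h | Next mark |
|---|---|---|---|
| Table 2 (SC, healthy) | 11 | all blank | 168 h |
| Table 3 (SC, ITP) | 11 | all blank | 168 h |
| Table 14 (SC, ITP, Czech) | 11 | all blank, also Day 7 | 168 h |

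The 11 marks are at 0, 0.5, 1, 3, 3.5, 4, 5, 6, 8, 12 and 24 h.

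- Gap between assessments: 168 − 24 = 144 h, or 6 days.
- Assessments after 24 h and up to 48 h: 0. The 24 h mark is the opening edge of the onset window.
- Part of the SC review period with no site check: 96 − 24 = 72 h, which is 72/96 = 75% of it.

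**Do other scheduled items inspect the site in the gap?**

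- Tables 2 and 3 schedule no physical examination between Day -1 and Day 8.
- Table 14 adds examinations during confinement, but its footnote d leaves the additional ones to the investigator's discretion. Under Section 8.2.1 a complete examination includes skin; the minimum content of a brief one does not.
- Vital signs are scheduled at 36 and 48 h and a PK sample at 96 h, so staff are with the participant then, but no site inspection is specified.

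**Effect of adding 36, 48 and 96 h.** Assessments after 24 h and up to 48 h rise from 0 to 2; those after 24 h and up to 96 h rise from 0 to 3. The longest interval before Day 8 falls from 144 h to 168 − 96 = 72 h.

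**Who is affected.** Section 4.1 makes Cohorts 7-14 the SC cohorts. Table 4 shows 4 + 8 + 8 = 20 participants dosed in Cohorts 7-9 and Cohort 10 in progress. Cohorts 11-14 are not yet dosed and would add 8 + 4 + 3 + 3 = 18 to 8 + 8 + 6 + 6 = 28, if all are run.

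**Grading passages side by side.** Section 6.8 defines the reaction by erythema, induration, ecchymosis, pain and pruritus. Appendix 11 grades on whether interruption or intervention is indicated, on transience or prolongation, and on hospitalization or threat to life; it names none of the five signs. Appendix 3 intensity applies to every AE. Ecchymosis at the site in an ITP participant fits both the Section 6.8 definition and the bruising criterion in Section 6.6, and no precedence is stated.

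**The case against.** The strongest reply is that reactions will be recorded anyway. Participants are confined through Day 8 and AE monitoring runs unbroken across the gap. Section 8.3.1.2 requires directly observed as well as spontaneously reported AEs to be entered, and Section 8.3.3 requires follow-up to resolution or stabilization. Pain and itch are reported by the participant, and unplanned evaluations are allowed. All of this stands. A reader might infer that late reactions or their peak severity will be missed; the documents do not support that. They support under-ascertainment: detection and timing after 24 h rest on reports and incidental observation, not on a fixed inspection.

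A second reply is that the onset statement justifies checks at 36 and 48 h only. That also stands. The case for 96 h rests instead on the SC review period, and nothing in the documents calls for 72 or 120 h.

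On grading, a reader might infer that Appendix 11 makes a large untreated induration Grade 1, or that its grades simply follow the treatment given. It does not say so: Grade 1 must be mild and transient, Grade 2 turns on intervention being indicated, and Grade 3 covers prolonged reactions. A reader might also infer that Appendix 11 grades drive the Section 6.6 rules generally. That is too broad. The pro-inflammatory criteria point to Appendix 9, the ITP bruising criterion cites CTCAE 4.03 without naming Appendix 11, and the general Grade 2 pause applies only where the investigator and Sponsor judge the event to be of concern.

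**Conclusion.** The timing point holds. All three SC schedules leave 144 h without a scheduled injection-site assessment. That gap takes in all of the stated 24-48 h window beyond its opening edge, and the last 72 h of the 96 h review. The consequence is less systematic and less precisely timed data on SC local tolerability, softened by confinement, continuous AE monitoring and, at Czech sites, discretionary examinations. It is a worthwhile, cheap improvement and not a failure of safety surveillance.

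The grading point holds only as an unreconciled set of instructions: Sections 6.8 and 8.3 with Appendix 11, Appendix 3, and the ITP bruising criterion in Section 6.6. The documents do not say which grade a local injection-site sign receives.

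The finding assumes that the table columns are read correctly. In the text version of Tables 2, 3 and 14 the row carries one cell more than the hour header. The extra cell falls after 336 h, so it affects the placement of the last two visits and not the 24 h or 168 h marks. No reaction rate is assumed, so the number of reactions affected is not estimated.

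**What to change.** 1. In Tables 2, 3 and 14, add the SC injection-site assessment at 36 and 48 h, and at 96 h to match the SC safety review.
2. Reconcile Section 6.8, Section 8.3, Appendix 11, Appendix 3 and the ITP bruising criterion in Section 6.6, and state which grade applies to local injection-site signs. Because Section 6.8 ties management to the grade, the choice of scale and any management rule belong to the sponsor; none is proposed here.

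The cost is a schedule and wording amendment and three brief inspections per participant while already confined. SC participants dosed after the change will have more site data than the 20 in Cohorts 7-9 and any Cohort 10 participants dosed before it. Summaries across SC cohorts should therefore state which schedule applied, since a higher recorded rate in later cohorts could partly reflect closer looking.

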6.9. Intervention After the End of the Study

No intervention will be provided to study participants at the end of the study.

7. DISCONTINUATION OF STUDY INTERVENTION AND PARTICIPANT DISCONTINUATION/WITHDRAWAL

Discontinuation of Study Intervention

Potential Cases of Acute Kidney Injury

Abnormal values in serum creatinine (SCr) concurrent with presence or absence of increase in blood urea nitrogen (BUN) that meet the criteria below, in the absence of other causes of kidney injury, are considered potential cases of acute kidney injury and should be considered important medical events.

An increase of ≥ 0.3 mg/dL (or ≥ 26.5 $\mu\text{mol/L}$) in SCr level relative to the participants own baseline measurement should trigger another assessment of SCr as soon as practically feasible, preferably within 48 hours from awareness.

If the second assessment (after the first observations of ≥ 0.3 mg/dL [or ≥ 26.5 $\mu\text{mol/L}$] in SCr relative to the participants own baseline measurement) is ≥ 0.4 mg/dL (or ≥ 35.4 $\mu\text{mol/L}$), adequate, immediate, supportive measures taken to correct apparent acute kidney injury.

Participants should return to the investigator site and be evaluated as soon as possible, preferably within 48 hours from awareness of the second assessment confirming abnormal SCr result. This evaluation should include laboratory tests, detailed history, and physical assessment. In addition to repeating SCr, laboratory tests should include serum BUN, serum creatine kinase, and serum electrolytes (including at a minimum potassium, sodium, phosphate/phosphorus, and calcium), in addition to urinary dipstick, urine microscopic examination, and urinary indices. Continued follow-up per protocol as well as any additional specific investigations/management required to manage the kidney injury is required until resolution.

All cases confirmed on repeat testing as meeting the laboratory criteria for acute kidney injury, with no other cause(s) of laboratory abnormalities identified, should be considered potential cases of drug-induced kidney injury irrespective of availability of all the results of the investigations performed to determine etiology of the abnormal SCr. If ≥ 2 healthy participants in a given cohort are noted to have 2 *consecutive* SCr results of ≥ 0.3 mg/dL (or ≥ 26.5 $\mu\text{mol/L}$), an assessment of whether the finding may be considered an adverse drug reaction should be undertaken.

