4. STUDY DESIGN

4.1. Overall Design

This is a Phase 1, randomized, double-blind, Sponsor-open, placebo -controlled, first-in-human single -ascending dose study to evaluate the safety, tolerability, and PK of PF-06755347 in healthy adult male participants by IV and SC administration and in male or female participants with persistent or chronic ITP by SC administration. Personnel, trained in advanced cardiac life support, emergency resuscitative equipment and the management of anaphylaxis, are immediately available to treat systemic reactions under the supervision of a physician. IV fluids, epinephrine, antihistamine and methylprednisolone will be available for immediate parenteral use in the event of an anaphylactic reaction.

A schematic of the overall study design is provided in [Section 1.2](#) (note actual dose levels to be administered beyond the starting dose are subject to change, see [Section 4.2.1.3](#)). A total of approximately 75 healthy adult male participants are planned to be randomized to either receive PF-06755347 or placebo by intravenous or subcutaneous administration in a 3:1 allocation ratio. All participants with ITP will receive PF-06755347. Clinical data from the IV cohorts supporting the transition to SC dosing are summarized in the IB, Section 6. SC Cohorts 7-14 are planned, Cohort 7 will have 4 male participants (3 active and 1 placebo)

and Cohorts 9-11 will have 8 male participants (6 active and 2 placebo). Cohort 12 (optional Japanese cohort) will include approximately 4-8 male Japanese healthy participants and Cohorts 13 and 14 combined will include a maximum of 12 male or female participants with ITP. The total number of participants randomized will not exceed 87. The ITP cohort dosing will start after completion of the 50 mg dose cohort in HPs.

Participants within each cohort will be dosed using a sequential dosing scheme. For all cohorts, only a single participant will be dosed at any given time. Based on the emerging safety data to date with IV dosing, cytokine and laboratory abnormalities reach their peak levels within the first few hours following PF-06755347 C_{max} and are resolved within 24 hours. The C_{max} was predicted to be 24 -48 hours with SC administration, however preliminary data from Cohort 7 supports increasing the monitoring period to 96-hr for safety.

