16. Exposure to live vaccines within the 28 days prior to the screening visit.
17. Treatment with an investigational drug within 30 days (or as determined by the local requirement) or 5 half-lives preceding the first dose of investigational product (IP) (whichever is longer). An approved COVID-19 vaccine is considered a concomitant medication. Due to the potential for interference with vaccine efficacy, the last dose of an approved COVID-19 vaccine must be completed 28 days prior to dosing with PF-06755347.
18. Screening supine BP ≥ 140 mm Hg (systolic) or ≥ 90 mm Hg (diastolic), following at least 5 minutes of supine rest. If BP is ≥ 140 mm Hg (systolic) or ≥ 90 mm Hg (diastolic), the BP should be repeated 2 more times and the average of the 3 BP values should be used to determine the participants eligibility.
19. Screening supine 12-lead ECG demonstrating a corrected QT (QTc) interval > 450 msec or a QRS interval > 120 msec. If QTc exceeds 450 msec, or QRS exceeds 120 msec, the ECG should be repeated 2 more times and the average of the 3 QTc or QRS values should be used to determine the participants eligibility.
20. Participants with **ANY** of the following abnormalities in clinical laboratory tests at screening or on admission, as assessed by the study specific laboratory and confirmed by a single repeat tests, if deemed necessary:
 - Aspartate aminotransferase (AST) or alanine aminotransferase (ALT) level $> 1.25 \times$ upper limit of normal (ULN);
 - Total bilirubin level $> 1.0 \times$ ULN; participants with a history of Gilberts syndrome may have direct bilirubin measured and would be eligible for this study provided the direct bilirubin level is \leq ULN;
 - Creatinine levels $> 1.0 \times$ ULN;
 - eGFR of < 90 mL/min/1.73m².
21. Male participants with partners currently pregnant; fertile male participants who are unwilling or unable to use a condom or whose female partners are unable or unwilling to use a highly effective method of contraception as outlined in this protocol for the duration of the study through final study release of the participant (inclusive of final extended immune follow-up visit, if required), or through at least 28 days after the last dose of IP (whichever is longer).
22. Blood donation (excluding plasma donations) of approximately 1 pint (500 mL) or more within 60 days prior to dosing.

23. Unwilling or unable to comply with the criteria in the [Lifestyle Considerations](#) section of this protocol.

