3. A single occurrence of confirmed drug induced liver injury (see [Appendix 6](#)) or confirmed drug induced kidney injury (see [Section 7.1](#)) will be reported as a serious adverse event, and therefore, will be considered dose limiting.

In the event of a dose **pause**, all available safety, PK (if available), cytokine, and complement data for the participants will be reviewed by the dose escalation subteam. The subteam should determine whether clinical symptoms associated with the pause criteria have resolved and determine whether IL-6 has returned to near baseline levels ie that the event is reversible. IL-6 has been selected as the surrogate marker for decision making purposes as it appears to be the most sensitive cytokine pathways from the non-human primate and human in vitro data. However, TNF- α , IFN- γ cytokine and complement data will be available at the time of review. If the dose escalation subteam determines that dosing may resume, a plan that mitigates risks to participants with the resumption of dosing may be implemented. Such a plan could include a revision of inclusion/exclusion criteria, repeating or reducing the dose, reducing infusion/dosing rate or adding appropriate safety monitoring or prophylactic treatment. This mitigation plan may need to be discussed with the Institutional Review Board (IRB) or Regulatory Authority as appropriate. The ultimate decision to continue dosing of study participants rests with the PI. Sponsor dose escalation subteam cannot overrule PI decision/clinical judgement.

If the decision is to **stop** dose progression this will also stop any further dose escalation.

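### The Section 7 cohort kidney trigger omits the rise from baseline, so read literally a normal creatinine meets it in essentially every healthy cohort

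*Protocol*

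**What the plan says.** Protocol Section 7, under potential cases of acute kidney injury, uses 0.3 mg/dL (26.5 µmol/L) three times.

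- **Individual trigger.** An increase of that size "in SCr level relative to the participants own baseline measurement should trigger another assessment of SCr".
- **Repeat test.** The next paragraph refers back to that event ("after the first observations of ≥ 0.3 mg/dL"), again relative to the participant's own baseline, and sets 0.4 mg/dL (35.4 µmol/L) for the second assessment. The work-up that follows is timed from "awareness of the second assessment confirming abnormal SCr result".
- **Cohort trigger.** At least two healthy participants in a cohort, each with two consecutive "SCr results of ≥ 0.3 mg/dL" (the µmol/L value is repeated). The consequence is that "an assessment of whether the finding may be considered an adverse drug reaction should be undertaken".

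For healthy participants, Section 5.2 excludes creatinine above the upper limit of normal and eGFR below 90 mL/min/1.73 m². It sets no lower bound on creatinine.

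**The concern.** The third use drops both the word for a rise and the reference to baseline. It speaks of results, which ordinarily means measured values, and restates its own threshold in both units instead of pointing back to the individual criterion. On its face it is an absolute cut-off that ordinary creatinine values exceed, and nothing in the entry criteria keeps participants below it.

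A trigger that is met whether or not creatinine has moved cannot separate a cohort with a kidney signal from one without. The error runs towards over-triggering, so no signal would be missed. A site that follows the text would record an assessment for nearly every healthy cohort. A site that applies the likely intent would be departing from the text.

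**Working it through.** **1. Is the number itself intact?** With the standard conversion of 88.4 (not in the documents), 0.3 × 88.4 = 26.5 and 0.4 × 88.4 = 35.4 µmol/L. Both unit pairs agree with the protocol. Only the baseline reference is missing.

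**2. Is the trigger defined elsewhere?** No. Section 6.6 makes "confirmed drug induced kidney injury" dose limiting and points to Section 7.1, but Section 7.1 contains no creatinine criterion. Section 6.7 has a general laboratory-abnormality rule without a creatinine threshold. SAP Section 6.2.2 refers laboratory abnormalities to sponsor reporting standards. Section 7 is the only source of the creatinine thresholds.

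**3. How often does it fire?** Let p be the chance that one participant has two consecutive qualifying results, and n the number of healthy participants in the cohort. The sentence is not limited to those on active drug, so n counts everyone. Then

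P(fires) = 1 − (1 − p)^n − n·p·(1 − p)^(n−1).

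Cohort sizes come from protocol Table 4 and Sections 4.1 and 9.2: 4, 5 and 8. For example, with p = 0.80 and n = 4: 1 − 0.0016 − 0.0256 = 0.9728. The documents do not give p, so it is shown as a range:

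| p | n = 4 | n = 5 | n = 8 |
|---|---|---|---|
| 0.50 | 68.8% | 81.3% | 96.5% |
| 0.80 | 97.3% | 99.3% | 99.99% |
| 0.95 | 99.95% | 99.997% | >99.999% |
| 0.99 | >99.999% | >99.999% | >99.999% |

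Setting P(fires) = 0.05 and solving gives p = 9.8% (n = 4), 7.6% (n = 5) and 4.6% (n = 8). The 5% is a yardstick chosen here; the protocol sets no such target. For the literal trigger to be that specific, fewer than about one healthy participant in ten could have two consecutive creatinine results at or above 0.3 mg/dL.

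**4. What is p plausibly?** All inputs here are assumptions: person means averaging 0.8, 0.9 or 1.0 mg/dL; between-person SD 0.10, 0.15 or 0.20; within-person CV 5, 8 or 10%; no drug effect. That makes 27 scenarios, each simulated with 13 and with 14 post-dose samples, because the chemistry row of Table 2 appears to show 14.

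| Reading | p per participant | fires, n = 4 | fires, n = 8 |
|---|---|---|---|
| As written (absolute level) | 99.4–100% | >99.999% | >99.999% |
| As a rise from own baseline | 0–2.7% | 0–0.4% | 0–1.8% |

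The upper end of the second row comes from the highest mean, SD and CV.

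**5. Cruder cross-check.** Take creatinine as normal with mean 0.7 to 1.0 and SD 0.1 to 0.2 mg/dL, and treat the two results as independent. The worst case is mean 0.7, SD 0.2: the chance that one result reaches 0.3 is 0.977, so p = 0.977² = 0.955, and the literal trigger still fires in 99.96% of cohorts of 4.

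**The case against.** The strongest reply is that context settles the meaning. The section defines the criterion in full once, as an increase over baseline; later uses are shorthand with the same unit pair; and the cohort sentence directly follows one about cases confirmed against the laboratory criteria. It also asks about a finding, and a normal creatinine is not one. This is a fair account of what was meant, and a rise is very likely the intent. It does not change what the sentence says, and a safety threshold should not depend on the reader supplying the missing condition.

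The second reply is that little follows from over-triggering. That stands. The consequence is an assessment, and the trigger is not among the pause, stop or termination criteria. The individual baseline-relative rule, the dose-limiting rule for confirmed drug-induced kidney injury (Section 6.6) and the 50% laboratory-abnormality rule (Section 6.7) operate independently. The assessment itself could also sort out a false trigger.

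Third, few cohorts remain. Table 4 shows Cohorts 1 to 9 dosed, Cohort 10 in progress, and 11 and 12 optional and not done; 13 and 14 enrol participants with ITP, outside a rule about healthy participants. A correction therefore bears on at most three healthy cohorts: two of 8 and one of 4 to 8. That limits the benefit but does not make the sentence right.

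Finally, the rows for p = 0.50 and 0.80 are unrealistically low. They are there to show that the result does not hinge on the assumed distribution.

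**Conclusion.** The point holds, as a minor error in the wording. As written, the cohort trigger is an absolute creatinine of 0.3 mg/dL and would be met in essentially every healthy cohort, with or without a drug effect. As a baseline-relative rule it would fire in at most about 0.4% of signal-free cohorts of 4 and 1.8% of cohorts of 8.

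The wording defect rests on the text alone. The percentages rest on assumed creatinine values, and the near-certainty of firing holds across every distribution tried. No claim is made that a repeat value back at baseline would require a work-up, since that step depends on a confirmed abnormal result.

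**What to change.** Reword the cohort trigger in Section 7 so that each of the two or more healthy participants must have *two consecutive SCr increases of ≥ 0.3 mg/dL (≥ 26.5 µmol/L) relative to the participant's own baseline*.

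Optionally, for consistency, state the repeat-test threshold as *an increase of ≥ 0.4 mg/dL (≥ 35.4 µmol/L) relative to the participant's own baseline*. At present the baseline reference in that sentence sits in the parenthesis about the first observation.

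The cost is a few words in one sentence, or two with the optional edit, which can go into the next amendment or administrative clarification. No samples, visits or participants are added.
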